17.3.1 Dosing Compliance

Descriptive statistics will be used to summarize test article compliance for each analysis population. Compliant subjects are defined as those who apply at least 75% and no more than 125% of the expected test article applications, and did not miss scheduled applications for more than 3 consecutive days. The percentage of compliant subjects will be also presented.

17.3.2 Efficacy Analyses

The efficacy analyses will be conducted on the mITT and PP populations.

17.3.2.1 Primary Efficacy Analyses

For each of the co-primary endpoints (percent change from Baseline at Week 12 in the inflammatory lesion counts and in the non-inflammatory lesion counts), the 90% confidence interval of the ratio of the mean percent reduction in lesion counts between the

GDC 268 group and the Reference Product group will be assessed in the PP population. If the 90% confidence intervals are contained within the interval [0.8, 1.25] for both inflammatory and non-inflammatory lesions, bioequivalence between GDC 268 and the Reference Product will be demonstrated.

The percent change from Baseline at Week 12 in the inflammatory lesion counts and in the non-inflammatory lesion counts for each GDC 268 and Reference Product group will be compared against VEH group at an $\alpha=0.05$ ($p<0.05$) in the mITT population using last observation carried forward (LOCF) imputation using analysis of variance (ANOVA) with factor of treatment in the statistical model using original percent change values.

If the distribution of percent change from Baseline in the lesion counts are significantly skewed, the analyses will be performed based on rank transformed data.

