
Statistical Methods
	
All statistical processing will be performed using SAS® Version 9.4 unless otherwise stated.
 
Study Populations: The Safety population will include all randomized subjects who applied at least one dose of test article.

	
The mITT population will include all randomized subjects who applied at least one dose of test article.
 
The PP population will include all mITT subjects who met all inclusion/exclusion criteria, were compliant with the assigned test articles based on the subject diaries (applied at least 75% and no more than 125% of the expected test article applications for the specified duration of the study), did not miss the scheduled test article applications for more than 3 consecutive days (i.e., 3 consecutive days with no test article application), have no other evidence of material dosing noncompliance, and completed the primary endpoint evaluation at Week 12 within the designated visit window (Day 85 ± 4 days) with no protocol violations that would affect the treatment evaluation including use of the prohibited medications.
 
Subject randomization will be stratified by the number of non-inflammatory lesions (≤ 70 / > 70) present at the Baseline Visit in order to ensure balanced enrollment of subjects across the treatment groups by non-inflammatory lesion count. No subset analyses are planned based on baseline non-inflammatory lesion counts.
 
Dosing Compliance: Descriptive statistics will be used to summarize test article compliance for each analysis population. Compliant subjects are defined as those who apply at least 75% and no more than 125% of the expected test article applications, and did not miss scheduled applications for more than 3 consecutive days. The percentage of compliant subjects will be also presented.
 
Efficacy Analyses: The efficacy analyses will be conducted on the mITT and PP populations.
 
Primary Endpoints For each of the co-primary endpoints (percent change from Baseline at Week 12 in the inflammatory lesion counts and in the non-inflammatory lesion counts), the 90% confidence interval of the ratio of the mean percent reduction in lesion counts between the GDC 268 group and the Reference Product group will be assessed in the PP population. If the 90% confidence intervals are contained within the interval [0.8, 1.25] for both inflammatory and non-inflammatory lesions, bioequivalence between GDC 268 and the Reference Product will be demonstrated.
 
The percent change from Baseline at Week 12 in the inflammatory lesion counts and in the non-inflammatory lesion counts for each GDC 268 and Reference Product group will be compared against VEH group at an $\alpha=0.05$ ($p<0.05$) in the mITT population using last observation carried forward (LOCF) imputation using analysis of variance (ANOVA) with factor of treatment in the statistical model using original percent change values.
 
If the distribution of percent change from Baseline in the lesion counts are significantly skewed, the analyses will be performed based on rank transformed data.

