3. OBJECTIVE

The objective of the study is to evaluate the safety, tolerability, and therapeutic equivalence of GDC 268 to Clindamycin Phosphate Topical Lotion, 1% and to compare the efficacy of these two products to the GDC vehicle lotion (i.e., placebo) in the treatment of acne vulgaris.

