4. STUDY DESIGN

This is a multicenter, randomized, double-blind, placebo-controlled, parallel group comparison study of GDC 268 and Clindamycin Phosphate Topical Lotion, 1% (GREENSTONE[®] BRAND) in healthy male and non-pregnant, non-breastfeeding female subjects 12 to 40 years of age (inclusive) with facial acne vulgaris. Eligible subjects must have a clinical diagnosis of facial acne vulgaris with an Investigator's Global Assessment (IGA) score of at least 2 (mild), a minimum of 25 but no more than 100 non-inflammatory lesions (open and closed comedones), a minimum of 20 but no more than 70 inflammatory lesions (papules and pustules) and ≤ 2 nodulocystic lesions (nodules and cysts) on the face at Baseline. Approximately 1200 subjects will be enrolled at approximately 50 study sites. Subjects will be randomized to one of three treatment groups on a 2:2:1 basis as follows:

1. GDC 268 (Gage) (generic clindamycin phosphate topical lotion)
2. Clindamycin Phosphate Topical Lotion, 1% (GREENSTONE[®] BRAND) (Reference Product)
3. GDC Vehicle (Gage)

All subjects will be instructed to apply the assigned test article twice daily to the entire face, once in the morning and once in the evening, for 12 weeks. The study will consist of a Screening/Baseline Visit, a follow-up telephone call at Week 2, and follow-up visits at Weeks 4, 8, and 12/End of Study (EOS) or Early Termination (ET). An unscheduled in-office follow-up visit may be completed at the discretion of the investigator for subjects with tolerability issues or a material adverse event (AE) concern. At EOS, safety and efficacy outcome measures will be compared to a) determine if treatment with GDC 268 is clinically equivalent to the currently marketed Clindamycin Phosphate Topical Lotion, 1% and b) both clindamycin phosphate 1% topical lotions are statistically superior in comparison to the GDC Vehicle.

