17. STATISTICAL CONSIDERATIONS

17.1 Sample Size

Based on the assumption of a 40% reduction in inflammatory and non-inflammatory lesions counts for the Reference Product and a 38% reduction for GDC 268, 346 PP subjects per active arm will provide 85% probability of demonstrating therapeutic equivalence between the two active treatments at an $\alpha=0.05$ (two one-sided tests) with 90% confidence interval bounds of the ratio of means being 0.08 and 1.25. Assuming a 25% reduction in inflammatory and non-inflammatory lesions counts for the VEH, 231 mITT subjects in the VEH arm and 462 mITT subjects in each of the active treatment arms will provide at least an 85% probability of demonstrating that each active treatment is statistically superior to vehicle treatment at a two-sided α of 0.05. Therefore, approximately 1200 subjects will be enrolled using a 2:2:1 randomization ratio (GDC 268: Reference Product: VEH) to obtain a total of 1155 mITT subjects and 865 PP subjects.

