17.3.2.5 Multiple Comparisons / Multiplicity

Not applicable.

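### Superiority to vehicle is tested but is not a condition of the bioequivalence conclusion, so equivalence can be declared in a trial that did not separate active drug from vehicle

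*Combined protocol and SAP*

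**What the plan says.** Section 17.3.2.1 gives the decision rule for the per-protocol (PP) population. The 90% CI for the test-to-reference ratio must fall between 0.8 and 1.25 on each lesion count. Once that is met "for both inflammatory and non-inflammatory lesions, bioequivalence between GDC 268 and the Reference Product will be demonstrated". The synopsis (Statistical Methods, Primary Endpoints) repeats it. Both state a sufficient condition with nothing added.

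The vehicle comparison follows in a separate paragraph of 17.3.2.1. Each active is compared with vehicle at p<0.05 "in the mITT population using last observation carried forward (LOCF) imputation using analysis of variance (ANOVA) with factor of treatment". That paragraph attaches no consequence to the result.

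Elsewhere superiority is clearly part of the study:

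- Section 3 includes in the objective "to compare the efficacy of these two products to the GDC vehicle lotion".
- Section 4 lists as item b), beside equivalence as item a), that "both clindamycin phosphate 1% topical lotions are statistically superior in comparison to the GDC Vehicle".
- Section 17.1 powers the study to show that "each active treatment is statistically superior to vehicle treatment".

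None of these ties superiority to the equivalence conclusion. Section 17.3.2.5 on multiplicity says only "Not applicable", and no joint success rule appears anywhere in the document.

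**The concern.** Two actives can show similar percent reductions because both work, or because every arm improves for reasons unrelated to the drug. Only the vehicle arm tells these apart. The plan itself expects a sizeable non-drug response: 25% on vehicle against 38–40% on active (17.1).

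The mechanism at issue is a good response in every arm. The ratio of two substantial, similar means is estimated precisely, so its CI fits easily inside [0.8, 1.25] whether or not the drug contributed. A weak or noisy response works the other way, because it widens the ratio CI and makes the rule harder to meet.

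As written, a trial in which neither active beat vehicle would still count as having demonstrated bioequivalence. The sponsor would then have to decide after unblinding how to treat the failed comparison.

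**Working it through.** **Inputs from the plan.** True reductions are 38% (test, T), 40% (reference, R) and 25% (vehicle). There are 346 PP subjects per active arm, and mITT numbers are 462, 462 and 231 (17.1). Equivalence uses two one-sided 5% tests; superiority is two-sided 5%. The limits are 0.8 and 1.25 (17.3.2.1).

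**Assumptions.** The SD σ is not stated. It is taken as equal in all arms and both endpoints. PP is nested in mITT with the same means. The endpoint correlation is 0 to 0.5. The CI is of Fieller form on untransformed data.

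**1. SD implied by the plan's 85% power.** With n = 346 per arm,

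Power ≈ Φ[(T − 0.8R)/(σ√(1.64/n)) − 1.645] + Φ[(1.25R − T)/(σ√(2.5625/n)) − 1.645] − 1,

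where 1.64 = 1 + 0.8² and 2.5625 = 1 + 1.25². The two square roots are 0.06885 and 0.08606. At σ = 32.3:

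- Lower limit: 6/(32.3 × 0.06885) = 2.698; less 1.645 gives 1.053; Φ = 0.854.
- Upper limit: 12/(32.3 × 0.08606) = 4.317; less 1.645 gives 2.672; Φ = 0.996.
- Power = 0.854 + 0.996 − 1 = 0.850.

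So σ ≈ 32.3 if 85% is per endpoint. If 85% is for both endpoints and they are independent, each needs √0.85 = 0.922, which gives σ ≈ 28.4. The scenarios below use 28.5 and 32.5, with 40 as a less favourable case that would contradict the stated 85%.

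**2. Planned superiority.** The standard error is σ√(1/462 + 1/231) = 0.0806σ, or 2.60 at σ = 32.3. For 38 vs 25, 13/2.60 ≈ 5.0 and power is Φ(5.0 − 1.96) ≈ 99.9%. This agrees with the plan's claim of at least 85%.

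**3. No drug effect, rule as written.** If every arm has true reduction m, the two contrasts standardise to the same value, and the pass probability per endpoint is 2Φ[0.2m/(0.06885σ) − 1.645] − 1.

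- m = 25, σ = 32.5: 5/2.238 = 2.235; less 1.645 gives 0.590; Φ = 0.722; pass probability 0.445. Two independent endpoints: 0.445² = 0.198.
- m = 40, σ = 32.5: 8/2.238 = 3.575; less 1.645 gives 1.930; Φ = 0.973; pass probability 0.946. Squared: 0.896.

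Simulation (400,000 trials per scenario, correlation 0 to 0.5) gives the probability that both CIs pass:

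| All arms at | SD 28.5 | SD 32.5 | SD 40 |
|---|---|---|---|
| 25% | 40–43% | 20–22% | 2–3% |
| 30% | 71–73% | 49–52% | 16–19% |
| 40% | about 97% | about 90% | 63–65% |

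If all four superiority tests (two actives, two endpoints) must also succeed, every cell falls to 0.1% or less. At correlation 0.8 the largest value found for equal arms was 0.3%.

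**4. Actives as planned (38/40), vehicle above 25%.** SD 28.5–32.5:

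| True vehicle reduction | Both CIs pass, at least one of four superiority tests fails | Both CIs pass, no superiority test succeeds |
|---|---|---|
| 30% | 8–16% | 0.0–0.3% |
| 33% | 49–55% | 1.3–7.8% |
| 35% | 69–80% | 14–27% |

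**5. Cost of the added condition at 38/40/25.** Probability of meeting the whole rule without and with it:

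| SD | Correlation 0 | Correlation 0.5 |
|---|---|---|
| 28.5 | 84.69% → 84.68% | 86.36% → 86.35% |
| 32.5 | 71.5% → 71.4% | 75.0% → 74.9% |
| 40 | 44.9% → 43.9% | 50.3% → 49.3% |

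**The case against.** The strongest reply is that superiority is plainly intended to count. Section 4 joins the two determinations with an *and*, section 17.1 powers both, and 17.3.2.1 places both under the primary analyses. The quoted sentence could be read as defining only the relative claim between the two lotions, with overall study success left unwritten. That may well be the intent. But the sentence states when bioequivalence is demonstrated, and no other text adds a condition. Section 2 says the design follows an FDA recommendation. Whether that source settles the matter cannot be checked here, and it would not supply the missing sentence in the plan.

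Four points about size stand:

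- If the vehicle response is truly 25%, both CIs pass with a failed superiority test in only about 0.1% of trials or less at the implied SD. The gap matters when the vehicle response is well above plan, and the document does not say how likely that is.
- In step 4, the middle column counts trials in which as few as one of four tests fails although both actives truly beat vehicle. Complete failure to separate is rarer, as the last column shows.
- The implied SD takes the lower limit as 0.8, as in the decision rule. Section 17.1 and the synopsis print 0.08 in the sample-size text. Taken literally, that implies an SD of about 52. The equal-arm pass rates would then be about 0% (all arms at 25%), 0.2–0.5% (30%) and 20–22% (40%).
- The figures do not cover the rank-transformed analysis that 17.3.2.1 allows for skewed data.

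These points bear on how often the gap would matter. They do not change what the rule says.

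**Conclusion.** The concern holds on the text alone. The bioequivalence rule rests on two equivalence CIs, and superiority to vehicle, though planned and powered, has no stated bearing on it.

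At the SD the plan implies (about 28–32 points with a 0.8 lower limit), a trial with no drug effect would meet the written rule in 20–43% of cases with all arms at 25%, and in about 90–97% with all arms at 40%. Larger SDs reduce these rates considerably. Under the planned effects the consequence is negligible. The added condition therefore guards against an unexpectedly high vehicle response and costs almost nothing otherwise. It should be made, but it does not undermine the design or the sample size.

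**What to change.** In 17.3.2.1 and in the matching synopsis paragraph, state that therapeutic equivalence is concluded only if both of these hold:

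- (i) both 90% CIs lie within [0.80, 1.25] in the PP population; and
- (ii) each active is superior to vehicle on both lesion counts in the mITT population (two-sided p<0.05, in the direction favouring active).

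Also state what is concluded if (i) holds and (ii) fails.

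In 17.3.2.5, keep the present entry and add the reason: every test must succeed (an intersection-union rule), so no alpha adjustment is needed.

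The cost is two or three sentences in two places, plus the one-line reason in 17.3.2.5. No extra subjects are needed. Section 17.1 states the equivalence and superiority powers separately, so neither figure has to change. The probability of meeting the whole rule falls by about 0.1 percentage point or less at SD 28.5–32.5, and by about 1 point at SD 40. The change should be made before unblinding.

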	
(e.g., prescription medication), require withholding or discontinuation of the application of the test article, or extend 2 cm beyond the Treatment Area will be documented as AEs. Any LSRs that are not listed above will be recorded as an AE.
 
Vital Signs Vital signs including temperature, systolic and diastolic blood pressure, heart rate, and respiration rate will be measured at Visit 1/Baseline. Assessments will be made after the subject has rested in a seated position for at least 5 minutes. Height and weight will also be measured at Visit 1/Baseline.
 
Urine Pregnancy Tests A UPT will be performed at Visit 1/Baseline and at Visit 5/Week 12/EOS for WOCBP.

Study Endpoints
	
Co-Primary Efficacy Endpoints:
 
 • Percent change from Baseline to Week 12 in the inflammatory (papules and pustules) lesion count. • Percent change from Baseline to Week 12 in the non-inflammatory (open and closed comedones) lesion count. 
Safety Endpoints:
 
 • Incidence (severity and causality) of any reported or observed treatment emergent AEs, whether or not they are considered to be related to the test article. • Number of subjects with improved/same versus worsened severities compared to Baseline of the following LSRs: erythema, edema, scaling/dryness, stinging/burning, pruritus, erosion, and pain at each onsite treatment visit.

Sample Size Calculations
	
Based on the assumption of a 40% reduction in inflammatory and non-inflammatory lesions counts for the Reference Product and a 38% reduction for GDC 268, 346 PP subjects per active arm will provide 85% probability of demonstrating therapeutic equivalence between the two active treatments at an alpha=0.05 (two one-sided tests) with 90% confidence interval bounds of the ratio of means being 0.08 and 1.25. Assuming a 25% reduction in inflammatory and non-inflammatory lesions counts for the VEH, 231 mITT subjects in the VEH arm and 462 mITT subjects in each of the active treatment arms will provide at least an 85% probability of demonstrating that each active treatment is statistically superior to vehicle treatment at a two-sided alpha of 0.05. Therefore, approximately 1200 subjects will be enrolled using a 2:2:1 randomization ratio (GDC 268:Reference Product:VEH) to obtain a total of 1155 mITT subjects and 865 PP subjects.

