7. RANDOMIZATION ASSIGNMENT

Subjects will be randomized on a 2:2:1 basis to one of three treatment groups:

1. GDC 268 (Test)
2. Clindamycin Phosphate Topical Lotion, 1% (Reference Product)
3. GDC Vehicle (Placebo)

The study will use a central randomization scheme and stratified by the number of non-inflammatory lesions (≤ 70 / > 70) present at the Baseline visit. Subjects who are eligible for enrollment into the study will be randomized at Visit 1/Baseline; subject kits will be dispensed according to the kit number assigned by an Interactive Web Response System (IWRS) as subjects are enrolled. Treatment group designation will remain blinded until the final database is locked (see [Section 15](#)).

A sealed copy of the randomization scheme should be retained at the study site and should be available to FDA investigators at the time of site inspection to allow for verification of the treatment identity of each subject.

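### The vehicle comparisons pool one residual variance across a 2:2:1 design, so their p-values are miscalibrated, in either direction, if vehicle and active spreads differ; separate variances per arm are a cheap safeguard

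*Combined protocol and SAP*

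**What the plan says.** Section 17.3.2.1 states that percent change from Baseline at Week 12, for each active arm and each lesion type, "will be compared against VEH group at an $\alpha=0.05$ ($p<0.05$) in the mITT population", with LOCF, "using analysis of variance (ANOVA) with factor of treatment in the statistical model using original percent change values". The synopsis repeats this. Section 17.1 makes the test two-sided.

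Section 7 sets the allocation: "Subjects will be randomized on a 2:2:1 basis to one of three treatment groups". Section 17.1 plans "231 mITT subjects in the VEH arm and 462 mITT subjects in each of the active treatment arms" and claims that these numbers "will provide at least an 85% probability of demonstrating that each active treatment is statistically superior to vehicle treatment". The planned means are "a 40% reduction in inflammatory and non-inflammatory lesions counts for the Reference Product and a 38% reduction for GDC 268" and, for vehicle, a 25% reduction.

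No SD is given, common or by arm. No separate-variance option, variance check or robust standard error is named. The one fallback in Section 17.3.2.1 is a rank transformation, used if the percent changes are significantly skewed. Section 17.3.2.4 plans no sensitivity analyses.

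**The concern.** A one-factor ANOVA estimates a single residual variance and applies it to every contrast. With unequal arms this matters, because the small arm dominates the true variance of the contrast while the large arms dominate the pooled estimate. More subjects at the same allocation do not cure it: the error depends on the allocation and the SD ratio.

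Equal spread is an unstated and unchecked assumption here. Percent change has a floor at -100% and no ceiling, and the plan puts vehicle further from that floor than the actives. A wider vehicle spread is therefore conceivable, though the documents do not show it.

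At stake is the calibration of the p-values for the two vehicle comparisons. Section 4 names superiority of both clindamycin lotions over vehicle as a study aim, and it is the trial's evidence that it can tell active drug from vehicle.

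**Working it through.** **Inputs.** From Sections 7, 17.1 and 17.3.2.1: vehicle 231, each active 462, two-sided alpha 0.05, mean reductions 40%, 38% and 25%, hence differences of 15 and 13 points. Assumed: the vehicle:active SD ratio r.

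**The plan's own figure.** The stated power of at least 85% cannot be reproduced without an SD. It is attainable: for 13 points it holds for any common SD up to 53.8. A likely value can be back-solved from the equivalence numbers (346 per arm, 85% power, limits 0.8 and 1.25 as in Section 17.3.2.1, one endpoint, two one-sided tests on the raw scale). With SD 32.28:
- Lower test: SE = 32.28 × √(1.64/346) = 2.22; (38 − 0.8×40)/2.22 − 1.647 = 1.05.
- Upper test: SE = 32.28 × √(2.5625/346) = 2.78; (1.25×40 − 38)/2.78 − 1.647 = 2.67.
- Power = Φ(1.05) + Φ(2.67) − 1 ≈ 0.85.

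That SD gives superiority power of 99.9% for 13 points. Other readings of the equivalence calculation give about 28 (85% jointly on both endpoints) or about 40 (log scale).

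**Weights.**
- Vehicle share of the contrast variance at equal SDs: (1/231)/(1/231 + 1/462) = 2/3.
- Vehicle share of the residual degrees of freedom: 230/1152 = 20%.

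**Case A: equal means, both actives with SD 1, vehicle with SD r.**
- Pooled variance = (230r² + 922)/1152.
- Model SE = √[pooled variance × (1/231 + 1/462)].
- True SE = √(r²/231 + 1/462).
- Actual error = 2[1 − Φ(1.96 × model SE/true SE)].

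| r | model SE / true SE | two-sided error |
|---|---|---|
| 0.8 | 1.105 | 3.0% |
| 1.0 | 1.000 | 5.0% |
| 1.1 | 0.956 | 6.1% |
| 1.25 | 0.899 | 7.8% |
| 1.4 | 0.852 | 9.5% |

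As a check, 20,000 simulated trials gave 7.6% at r = 1.25. A Welch comparison in the same simulations stayed at 4.9% to 5.0% for every ratio tried, from 1.0 to 2.0.

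**Case B: one active inert with the vehicle's mean and SD r, the other active effective with SD 1.** To get a value for r, suppose the SD scales with the fraction of lesions remaining: 0.75/0.62 = 1.21 and 0.75/0.60 = 1.25.
- Pooled variance = (691r² + 461)/1152.
- Model SE/true SE = √(pooled variance)/r.
- r = 1.21: √1.278/1.21 = 0.934, error 6.7%.
- r = 1.25: √1.337/1.25 = 0.925, error 7.0%.

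**Case C: both actives inert and distributed as vehicle.** All SDs are equal and the error is 5.0%.

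**Under the planned effect** (active SD 32.28, r = 1.25):
- True SE = 32.28 × √(1.5625/231 + 1/462) = 3.05; model SE = 0.899 × 3.05 = 2.74.
- 13 points: pooled power = Φ[(13 − 1.96×2.74)/3.05] = 99.4%; separate-variance power = Φ(13/3.05 − 1.96) = 98.9%.
- 15 points: 99.9% and 99.8%.

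**The case against.** One-factor ANOVA is a conventional prespecified choice, and nothing in the documents shows that the vehicle arm is more variable. Several points on this side stand.

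- A reader might infer that the 5% threshold fails for these comparisons. The documents do not support that. The scaling argument that yields ratios of 1.21 to 1.25 uses the means planned under an effect. If both products are inert, the same argument makes the SDs equal and the error is 5% (Case C). The 7.8% figure needs equal means together with a smaller spread in both active arms, which that argument does not produce.
- In Case B the true test-to-reference ratio would be well outside [0.8, 1.25] (for an inert test product, about 25/40 = 0.63), so equivalence would normally fail anyway.
- Section 4 wants both actives to beat vehicle. In Case A simulations, the chance that both pass on one endpoint was 1.5% at ratio 1 and 3.0% at 1.25. The per-comparison rate still governs each separate claim.
- A reader might also expect confidence intervals against vehicle to be affected. Section 17.3.2.1 plans none: its only interval is the test-to-reference ratio in the PP population, which the vehicle comparison does not feed.

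The rank fallback is a partial answer. A floor with no ceiling is also an argument for skewness, and ranking compresses a long upper tail. But the trigger is skewness, not unequal spread, and a one-factor analysis of ranks still pools one variance. The error rates above are normal-theory figures on the raw scale; none was calculated for ranks.

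**Conclusion.** The point holds as a conditional one of low severity. The planned model is sensitive to unequal spread because of the 2:2:1 allocation, and the plan neither states, checks nor relaxes the equal-variance assumption. The direction is open: too lenient if vehicle is more variable, conservative if it is less so.

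The size depends on SDs that the documents do not give. Over the scenarios shown for ratios of 0.8 to 1.25, two-sided error runs from 3.0% to 7.8%; it is 6.7% to 7.0% when one product is inert and the other works, and 5% when both share the vehicle distribution. With the planned 13 to 15 points and an SD near 32, the significance verdict would differ in fewer than one trial in a hundred. What would change is the reported p-value.

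**What to change.** In Section 17.3.2.1 and the synopsis, keep treatment as the only factor but specify a separate residual variance for each arm with Satterthwaite degrees of freedom (in SAS, PROC MIXED with a REPEATED statement and GROUP=treatment), or a Welch contrast of each active arm against vehicle. Apply it to both lesion counts and to any rank version. State the SD behind Section 17.1, by arm if known. Settle this before unblinding, so that the variance model is not chosen from the results.

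The cost is about one line of text and code. Power is essentially unchanged if spreads are equal. If vehicle is more variable, nominal power falls slightly: 99.4% to 98.9% at SD 32.28 and ratio 1.25. A reader might infer that power is safe whatever the SD; the documents do not support that. At an active SD of 53.8, the largest common SD compatible with the stated 85%, separate-variance power for 13 points at ratio 1.25 is 72.4%, against 78.6% pooled. Part of that gap is the leniency of the pooled test, and most of the shortfall from 85% comes from the extra vehicle variability, which lowers power under either method.

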17.3 Statistical Methods

All statistical processing will be performed using SAS® Version 9.4 unless otherwise stated.

The Safety population will include all randomized subjects who applied at least one dose of test article.

The mITT population will include all randomized subjects who applied at least one dose of test article.

The PP population will include all mITT subjects who met all I/E criteria, were compliant with the assigned test articles based on the subject diaries (applied at least 75% and no more than 125% of the expected test article applications for the specified duration of the study), did not miss the scheduled test article applications for more than 3 consecutive days (i.e., 3 consecutive days with no test article application), have no other evidence of material dosing noncompliance, and completed the primary endpoint evaluation at Week 12 within the designated visit window (Day 85 ± 4 days) with no protocol violations that would affect the treatment evaluation including use of the prohibited medications.

Subject randomization will be stratified by the number of non-inflammatory lesions (≤ 70 / > 70) present at the Baseline Visit in order to ensure balanced enrollment of subjects across the treatment groups by non-inflammatory lesion count. No subset analyses are planned based on baseline non-inflammatory lesion counts.

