17.3.2.4 Sensitivity Analysis

No sensitivity analyses are planned. Any additional analyses performed will be described in the final clinical study report.

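### Randomisation is stratified on baseline non-inflammatory count, but no stated efficacy model uses the stratum or a baseline count, which may cost precision in the equivalence test but not validity

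*Combined protocol and SAP*

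**What the plan says.** Section 7 has a central randomisation scheme "stratified by the number of non-inflammatory lesions", cut at 70, and the synopsis adds that it is blocked. Section 17.3 repeats this ("Subject randomization will be stratified by the number of non-inflammatory lesions"), gives balance between arms as the purpose, and rules out subset analyses by that count.

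Section 17.3.2.1 describes two analyses:

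- **Each active arm against vehicle** (mITT, LOCF): an "analysis of variance (ANOVA) with factor of treatment in the statistical model using original percent change values". The synopsis gives the same model.
- **Equivalence**: a 90% confidence interval for the ratio of mean percent reductions. The "GDC 268 group and the Reference Product group will be assessed in the PP population", against limits of 0.8 and 1.25 for both lesion types. No model, covariate or interval method is given.

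If the data are skewed, "the analyses will be performed based on rank transformed data", again with no model terms named. Section 17.3.2.4 states "No sensitivity analyses are planned". Both lesion counts are taken at Baseline on every subject (sections 9.1 and 10.2), but they enter the efficacy analysis only as the denominator of percent change.

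**The concern.** A stratification factor is normally chosen because it is thought to be prognostic. Stratified allocation removes part of the between-arm variation due to that factor. A treatment-only model still counts that variation as error, so its standard errors are somewhat too large. Baseline inflammatory count is not stratified on at all. Chance differences in it, and in non-inflammatory count within strata, are left unadjusted.

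The cost would fall on the sponsor's chance of showing equivalence, where there is least slack. The assumed reductions of 38% and 40% put the test arm 38 − 0.8 × 40 = 6 percentage points above the lower limit, and both endpoints must pass.

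Leaving the equivalence model unstated also leaves the choice of covariates open until after the data are seen, in a trial decided by whether an interval falls inside fixed limits.

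**Working it through.** **Inputs from section 17.1.** Reductions of 40% (reference), 38% (test) and 25% (vehicle); 346 per-protocol subjects per active arm; 462 and 231 mITT subjects per active and vehicle arm; one-sided 0.05 for each equivalence test, two-sided 0.05 for superiority. Equivalence limits of 0.8 and 1.25 are from section 17.3.2.1. Section 17.1 prints the lower limit as 0.08; 0.8 is used here because it is the limit the analysis applies.

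**Assumptions.** The documents give no SD of percent change and no R² for the baseline terms. R² is varied from 0 to 0.20.

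**Step 1: the plan's own figure.** Section 17.1 says "346 PP subjects per active arm will provide 85% probability of demonstrating therapeutic equivalence between the two active treatments". Without an SD this cannot be reproduced independently, so it is solved backwards. Equivalence is tested on T − 0.8R and 1.25R − T. With SD = 32.27:

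- Lower: 6 / [32.27 × √((1 + 0.8²)/346)] = 6 / 2.222 = 2.70
- Upper: (50 − 38) / [32.27 × √((1 + 1.25²)/346)] = 12 / 2.777 = 4.32

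With a critical value of about 1.647, the noncentral t distribution gives power of 0.850. An SD of about 32.3 therefore matches the stated 85% per endpoint.

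**Step 2: effect of adjustment.** Residual SD = 32.27 × √(1 − R²), 688 degrees of freedom; effective n = 346/(1 − R²).

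| R² | Cut in SE | Effective n per arm | Equivalence power |
|---|---|---|---|
| 0 | 0% | 346 | 85.0% |
| 0.01 | 0.5% | 349 | 85.3% |
| 0.04 | 2.0% | 360 | 86.3% |
| 0.09 | 4.6% | 380 | 88.0% |
| 0.20 | 10.6% | 432 | 91.4% |

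At other SDs, power at R² of 0 and 0.20 is 92.2% and 96.3% (SD 28.4, which applies if the 85% is joint over two independent endpoints), and 79.1% and 87.0% (SD 35).

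**Step 3: net gain over a treatment-only analysis.** Stratified allocation already gives a treatment-only test of non-inflammatory count part of this gain. Simulation of 30,000 trials per setting (Monte Carlo error about 0.2 points), assuming 40% of subjects above 70 lesions, uniform baseline counts within the entry ranges, and inflammatory count unrelated to the stratum, gives:

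| R² | Inflammatory, net gain (points) | Non-inflammatory, net gain (points) |
|---|---|---|
| 0 | 0 | 0 |
| 0.01 | 0.4 | 0.2 |
| 0.04 | 1.3 | 0.9 |
| 0.09 | 2.9 | 1.9 |
| 0.20 | 6.1 | 4.3 |

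**Step 4: validity.** In the same simulation, the treatment-only non-inflammatory test at a true ratio of 0.8 has size 4.9%, 4.7% and 3.9% at R² of 0.04, 0.09 and 0.20. A separate simulation (20,000 runs, 25% of subjects above 70, R² taken as that of the stratum) gives 4.5%, 4.3% and 3.4% at R² of 0.05, 0.10 and 0.20. There, the treatment-only ANOVA against vehicle has size 4.3%, 3.8% and 2.8% (nominal 5%). Error is not inflated.

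**Step 5: chance imbalance.** The SE of the test − reference difference is 32.27 × √(2/346) = 2.45. A 1-SE imbalance in a baseline count correlated 0.1 to 0.3 with response shifts that difference by 0.25 to 0.74 points, against 6 points of room.

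**Step 6: vehicle comparisons.** At SD 32.3, power for 38% against 25% with 462 and 231 subjects is 99.9% with or without adjustment.

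**Step 7: sensitivity to the printed 0.08.** If the sample size was really computed with a lower limit of 0.08, the back-solved SD is about 52. Vehicle power is then Φ(13/[52 × √(1/231 + 1/462)] − 1.96) = Φ(1.14), about 87%, and adjustment would matter there too.

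**The case against.** The case against runs as follows:

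- A treatment-only ANOVA is a legitimate choice. It is valid, it is stated identically in the synopsis and section 17.3.2.1, and the declared purpose of stratifying was balance, which the design delivers.
- The quoted model is for the vehicle comparisons, where at SD 32.3 adjustment changes nothing that matters. All the cost lies in the equivalence analysis, whose model is not stated.
- The size rests on an unstated SD, R², share above 70 lesions and baseline distribution. Percent change is already scaled to baseline, so a sizeable R² cannot be presumed. At R² of 0.01 to 0.04 the net gain is only 0.2 to 1.3 points per endpoint.
- Stratum and count overlap heavily for the non-inflammatory endpoint.
- The missing interval method could be cured by naming an unadjusted Fieller interval.

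Most of this stands as a limit on size. The plan is not invalid, the gain may be small, and nothing in the documents supports R² = 0.20. It does not remove the point. Dividing by baseline does not guarantee that percent response is unrelated to baseline count. The overlapping term costs one degree of freedom. An unadjusted Fieller interval would settle the specification but still leave unused the precision that collected, randomised-on data can offer.

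**Conclusion.** The concern holds. No stated analysis uses the stratification factor or a baseline count, and the equivalence analysis has no stated model. The possible loss is of precision in the equivalence test; omitting the terms does not inflate type I error.

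At the back-solved SD of about 32.3, and net of the benefit of stratified allocation, the simulated loss is 0.2 to 0.4 points of per-endpoint power at R² = 0.01, about 1 point at 0.04, 2 to 3 at 0.09 and 4 to 6 at 0.20. It is nil at R² = 0. These figures depend on the assumed SD, R², stratum share and baseline distributions, and on reading the lower limit as 0.8. The change should be made because it is cheap and because the equivalence model needs fixing in advance whatever R² turns out to be. It is not a condition for the trial's validity.

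**What to change.** In section 17.3.2.1 and the synopsis, before unblinding:

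1. Specify an ANCOVA with treatment, randomisation stratum (≤70 / >70) and the baseline count of the lesion type being analysed.
2. Use it for each active arm against vehicle in mITT.
3. Name it as the model for the test/reference ratio in the per-protocol population, with the adjusted means, their covariance and the model's error variance entering a Fieller 90% interval.
4. Carry the same terms into any rank-transformed analysis of the vehicle comparisons.
5. Keep the unadjusted analysis as supportive.

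The statistical price is one or two degrees of freedom out of about 690 (two active arms, per-protocol) or 1150 (mITT). All the data are already collected. The text sits in the protocol, so a formal amendment would need IRB approval under section 18.4, and it could be combined with any other pending change. The sponsor should also state the SD behind the sample size and reconcile the 0.08 printed in section 17.1 with the 0.8 in section 17.3.2.1, since the size of the gain depends on both.
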